### **7.5.8 Efficacy During Off-Treatment Follow-up**

The following binary endpoints are summarized by treatment regimen with response rates using NC = M at EOD (see [Section 8.5](#)) and each scheduled visit during off-treatment follow-up through Week 192 for off-treatment follow-up subjects in the Post-Year 1 Efficacy Cohort (see [Section 6.3](#)):

- HBV DNA < LOQ, LOQ - < 50, 50 - < 172, 172 - < 1,720, 1,720 - < 17,200 and  $\geq 17,200$  IU/mL
- HBeAg loss
- HBeAg seroconversion
- HBsAg loss
- HBsAg seroconversion
- ALT  $\leq 1 \times$  ULN,  $> 1 - 2 \times$  ULN,  $> 2 - 5 \times$  ULN, and  $> 5 \times$  ULN

In addition, the efficacy response shifts from EOD using an HBV DNA cut-off of 50 IU/mL are summarized at Weeks 24, 48, 72, 96 and 120 during off-treatment follow-up for off-treatment follow-up subjects in the Post-Year 1 Efficacy Cohort (limited to ETV, PBO OL, and All ETV). Efficacy response shift categories are defined as follows:

- Complete response: HBV DNA < 50 IU/mL, ALT normalization, and HBeAg seroconversion.

- Partial response: HBV DNA < 50 IU/mL and ALT normalization without HBeAg seroconversion (including missing HBeAg).
- Virologic response: HBV DNA < 50 IU/mL without ALT normalization and HBeAg seroconversion (including missing ALT or HBeAg).
- Non-response: HBV DNA  $\geq$  50 IU/mL.

Results are presented by total ETV duration: overall, < 2 years, and  $\geq$  2 years, using 102 weeks as 2 years.

Efficacy response shifts from EOD using an HBV DNA cut-off of 2000 IU/mL are also summarized analogously.

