Anti-HBV treatment of study subjects during LTFU shall be at the discretion of the treating clinicians and may include marketed or investigational products. In the event that a subject in LTFU develops an extreme elevation of ALT due to acute exacerbation of CHB, rescue open-label study ETV will be made available upon investigator request and after discussion and approval by the BMS Central Medical Monitor (see section 4.1.2). If ETV is initiated during the LTFU phase, HIV testing and monitoring is strongly recommended as ETV is not recommended in subjects co-infected with HIV and HBV unless the subject is also receiving effective anti-retroviral therapy. For subjects initiated on other anti-HBV treatment during LTFU, investigators should evaluate the need for HIV testing based upon standard of care and the product label for the selected agent.

At the end of the on study treatment phase, the sponsor will not continue to supply study drug to subjects/investigators unless the sponsor chooses to extend the study. The only exception is for subjects started on rescue open-label ETV as a consequence of an

extreme elevation of ALT due to acute exacerbation of CHB (see section 4.1.2). The investigator should ensure that the subject receives appropriate standard of care to treat the condition under study, if necessary.

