## 6 STUDY PERIODS, TREATMENT REGIMENS AND POPULATIONS FOR ANALYSES

### 6.1 Study Periods

Study periods for efficacy and safety analyses are defined as follows:

- **Pre-treatment period** begins at the first visit until initiation of study therapy.
- **On-treatment period** begins after the first day of study therapy and ends at the last dose of study therapy plus 5 days.
- **ETV treatment period** begins after the first day of active ETV and ends at the last dose of active ETV plus 5 days.
- **Off-treatment follow-up period** begins on the last dose of study therapy plus 6 days and ends at the start of alternative anti-HBV therapy minus 1 day.
- **Long-term follow-up period** begins on the last dose of study therapy plus 6 days until the end of the study.
- **Alternative ETV follow-up period** begins on the later of the last dose of study therapy plus 6 days and the start of alternative ETV therapy, until the end of the study.

Note that rescue open-label ETV is considered alternative anti-HBV therapy. See [Section 8.9](#) for additional conventions.

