### **7.5 Efficacy**

Efficacy endpoints are presented by as-randomized treatment regimen for treated subjects.

Binary efficacy endpoints are analyzed using 2 algorithms:

- Non-Completer = Failure (NC = F): The numerator is based on subjects meeting the response criteria. The denominator is based on treated subjects. Subjects who have missing data at the analysis week are considered as failures.
- Non-Completer = Missing (NC = M): The numerator is based on subjects meeting the response criteria. The denominator is based on subjects with data at the analysis week. Subjects who have missing data at the analysis week are excluded.

Treatment regimens are compared using a difference in proportions (ETV - PBO), 95% confidence interval (CI) and p-value based on  $NC = F$  for the primary endpoint and key secondary endpoints. Analyses are stratified by age randomization strata (see [Section 7.3.4](#)). The proportions are computed within each stratum, and combined using a weighted average with weights proportional to stratum size (Cochran-Mantel-Haenszel [CMH] weighting). ETV will be considered superior to PBO if the p-value is  $< 0.05$ . CIs for differences in proportions are based on the stratified normal approximation to the binomial distribution with unpooled proportions used in the computation of the standard error of the difference.

A two-stage testing procedure will be employed for testing the primary and key secondary endpoints using  $NC = F$ . In the first stage, the test for primary endpoint will be performed. Provided the test result of the primary endpoint is significant (p-value  $< 0.05$ ), the second stage tests of the key secondary endpoints will be conducted. Because the tests for the key secondary endpoints will be conducted sequentially only if the test for the primary endpoint is successful, significance levels will not be adjusted for the first stage testing. All tests for treatment comparison will be two-sided at a significance level of 0.05.

For binary composite endpoints involving several components (eg, primary efficacy endpoint), only subjects who meet the response criteria for all components are considered to be responders for the composite endpoint. In addition, subjects who meet the response criteria for some components but are missing other components are considered to be missing the composite endpoint.

See also [Sections 8.4 to 8.8](#) for additional conventions.

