#### **7.5.2.5 Sustained HBeAg Seroconversion During Off-Treatment Follow-up**

Response rates of HBeAg seroconversion are presented by treatment regimen at EOD (end of dosing) and each scheduled visit during off-treatment follow-up through Week 192 using  $NC = F$

and NC = M for the Year 2 Efficacy Cohort with HBeAg seroconversion at EOD. Rates using NC = F are shown only through off-treatment follow-up Week 48.

Treatment regimens are compared between treated subjects with HBeAg seroconversion at both on-treatment Week 48 and EOD (ETV S48 - PBO S48; NC = F) with a difference in proportions and p-value at off-treatment follow-up Week 24 at the final analysis, provided the test result of HBeAg seroconversion was significant at the primary analysis (see [Section 9](#)).

Sustained HBeAg seroconversion is summarized analogously with response rates using NC = M for the Post-Year 1 Efficacy Cohort with HBeAg seroconversion at EOD.

Sustained HBeAg seroconversion at off-treatment follow-up Week 24 is also summarized by subgroups for treated subjects with HBeAg seroconversion at EOD (see [Section 7.5.1](#)).

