### 8.4 Visit Week Windows

For longitudinal presentations, values are first selected within their respective study periods (see Section 6.1). Next, windows around scheduled measurement times are constructed based on the midpoint between scheduled measurement visits and the value closest to the scheduled visit for each measurement is selected from those that fall within the window.

Visit windows are defined in Table 8.4-1:

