- Dose end date of active ETV is the dose end date of study therapy for ETV-randomized subjects and the dose end date of open-label ETV for PBO-randomized subjects. This date is used to assess time on active ETV.
- Last dose date of active ETV is the dose end date of active ETV derived only when the last dose date of study therapy is not missing.
- Start date of rescue open-label ETV is the earliest start date of rescue open-label ETV identified from valid dosing records, ie, non-missing start date and total dose > 0, from rescue open-label ETV study medication CRFs.
- Start date of alternative ETV therapy is the earliest start date of (1) rescue open-label ETV, or (2) concomitant ETV taken on treatment or during long-term follow-up.
- Start date of alternative anti-HBV therapy is the earliest start date of (1) rescue open-label ETV, or (2) concomitant anti-HBV medication taken on treatment or during long-term follow-up.
- Last contact date is the death date, if it exists, or the latest of the following dates: randomization; first or last dose of study therapy; adverse event onset or resolution; hepatitis B related diagnosis; laboratory test (safety, pregnancy, serology and virology); liver biopsy; physical measurement; physical exam; neurologic exam; vital sign; non-study medication start or stop; last contact from end of treatment or end of study subject status; Tanner staging.

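### Off-treatment response rates shown as NC = M lose children who restart anti-HBV therapy, so they are optimistic where restart follows relapse

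*SAP*

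**What the plan says.** Four SAP rules combine.

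- **Period (6.1, 8.9).** Off-treatment follow-up "ends at the start of alternative anti-HBV therapy minus 1 day". Rescue entecavir counts as such therapy: "Start date of alternative anti-HBV therapy is the earliest start date of (1) rescue open-label ETV", or of any concomitant anti-HBV medication if that is earlier.
- **Selection (8.4).** For by-visit tables, "values are first selected within their respective study periods"; visit windows are applied only afterwards.
- **Missing data (7.5).** Under NC = M, "Subjects who have missing data at the analysis week are excluded". Under NC = F the same subjects are failures.
- **Outputs.** For the 7.5.8 HBV DNA categories, HBeAg and HBsAg endpoints and ALT categories: "The following binary endpoints are summarized by treatment regimen with response rates using NC = M at EOD". In 7.5.2.5 the Year 2 Efficacy Cohort has both algorithms, but "Rates using NC = F are shown only through off-treatment follow-up Week 48". The other summary there is NC = M only: "Sustained HBeAg seroconversion is summarized analogously with response rates using NC = M for the Post-Year 1 Efficacy Cohort with HBeAg seroconversion at EOD".

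The formal comparison of sustained seroconversion, at off-treatment Week 24, uses NC = F. The response-shift tables in 7.5.8 name no missing-data algorithm.

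On who restarts, Protocol 4.1.1 says: "Anti-HBV treatment of study subjects during LTFU shall be at the discretion of the treating clinicians". Protocol 4.1.2 ties sponsor-supplied rescue entecavir to extreme ALT elevation in a flare of hepatitis B.

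**The concern.** Restart of therapy after stopping is unlikely to be a random event. One documented route to it is a flare, and the other is a clinician's judgement of how the child is doing. If children who relapse are the ones re-treated, NC = M removes them from the table just when they would count as failures, and the remaining rate describes those who did well enough to stay untreated.

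Off-treatment hepatitis B serology is scheduled only at Week 24 and every 24 weeks (Protocol Table 6.1). A child who relapses and restarts between two such visits may therefore never appear as having lost seroconversion, unless unscheduled or local serology is captured.

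Durability of response off treatment is a stated secondary objective (Protocol 2.2), and sustained seroconversion is a key secondary endpoint (SAP 4.2). What is at stake is how far the long-term descriptive rates support a durability statement.

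**Working it through.** The plan states no off-treatment, relapse or restart rate, so there is no figure to reproduce. The check has two parts.

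**1. Trace of the rule.** A child stops study drug, later restarts on day D, and attends a visit after D. The period ended on day D - 1 (6.1, 8.9). The value is outside the period and is not eligible for a window (8.4). If no value before D lies in that window, the child has no data for that visit and NC = M excludes the child (7.5). A relapse measured before D is still counted as non-response at that visit. The SAP has no rule counting restart as non-response in the NC = M off-treatment rates.

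**2. Size.** Let r be the share of children restarted by the visit, s the displayed NC = M response, and q the proportion of restarters who would count as responders. With no other missing data:

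- Rate with restarters included = s(1 - r) + rq
- Overstatement = s - [s(1 - r) + rq] = r(s - q)

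All values of r, s and q below are assumptions. s = 75% illustrates children seroconverted at end of dosing (7.5.2.5). s = 20% illustrates 7.5.8, which covers all off-treatment subjects.

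| s | q | r = 10% | r = 20% | r = 30% |
|---|---|---|---|---|
| 75% | 0 | 7.5 | 15.0 | 22.5 |
| 75% | 50% | 2.5 | 5.0 | 7.5 |
| 75% | 75% | 0 | 0 | 0 |
| 20% | 0 | 2 | 4 | 6 |
| 20% | 10% | 1 | 2 | 3 |
| 20% | 20% | 0 | 0 | 0 |
| 20% | 50% | -3 | -6 | -9 |

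Entries are percentage points; positive means NC = M is too high. The gap cannot exceed r × s.

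In counts: 20 children are seroconverted at end of dosing, 4 restart, and 12 of the other 16 respond. NC = M shows 12/16 = 75%; restart as failure shows 12/20 = 60%.

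Cross-check by another route: suppose 30% relapse and half of these restart before the visit. NC = M shows 0.70/(1 - 0.30 × 0.50) = 0.70/0.85 = 82.4%, against 70.0%, a gap of 12.4 points. The formula agrees: r = 0.15, s = 0.824, q = 0 gives 12.4. If instead 20% restart at random with respect to relapse, NC = M shows 0.70 × 0.80/0.80 = 70%, with no bias.

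**The case against.** Several points on the other side stand.

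- **Ending at restart is coherent.** A child back on antivirals is no longer off treatment, and Protocol 8.4.2 closes the same period for safety at the same point. NC = M is also the protocol's rule for exploratory endpoints (8.4.3), so those tables are as pre-specified. Section 8.4.3 does not prescribe it for sustained seroconversion.
- **Much of the seroconversion gap is already covered.** SAP 6.3 places all treated subjects in the ETV and PBO groups of the Year 2 Efficacy Cohort. The end-of-dosing seroconverters in the Post-Year 1 summary therefore already have NC = F rates by randomized arm through off-treatment Week 48. What remains is the split into PBO BL, PBO OL and All ETV, and the later visits.
- **Restart is not invisible.** SAP 7.6.6.2 summarizes ALT by visit for both off-treatment and long-term follow-up, so the difference in n roughly indicates how many were measured after restart. Subjects with flares have ALT and HBV DNA plots (7.6.6.1). Time in off-treatment follow-up (7.4.1) and alternative medications (7.4.2) are summarized in aggregate. None of these tabulates restart by visit or links it to response.
- **Stopping NC = F at Week 48 is defensible.** With 264 weeks in all, a stop at Week 96, 144 or 192 leaves at most 168, 120 or 72 off-treatment weeks. Running NC = F on would count visits that could not occur as failures.
- **Direction is not certain.** A child can restart with HBeAg-negative disease while seroconversion is intact (Protocol 4.1.1 describes that state), which can make q larger than s.

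A reader might also infer that after Week 48 response appears only as NC = M. The documents do not support that: the shift tables run to off-treatment Week 120 and name no algorithm. They define no restarted category, but table formats are left to a Data Presentation Plan that is not available here.

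**Conclusion.** The mechanism is certain from the SAP's rules: the NC = M off-treatment rates lose restarted children at later visits, and are optimistic where restart follows relapse. It applies to the 7.5.8 binary and category rates, to the 7.5.2.5 rates after off-treatment Week 48, and to the Post-Year 1 summary for the groups and visits without an NC = F counterpart. For the category tables, optimistic means that the favourable HBV DNA and ALT categories are inflated.

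The size is unknown. Over the assumed range it runs from +22.5 to -9 points, zero included. The large values belong to children seroconverted at end of dosing; for 7.5.8 at an assumed 20% response the ceiling is 2 to 6 points.

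A reader might go further and conclude that the key secondary test or the NC = F durability rates are biased in the same way. They are not: NC = F makes a restarted child with no eligible value a failure. No formal test, alpha, NC = F rate or primary conclusion is affected. This is an inexpensive improvement to descriptive tables.

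**What to change.** Keep all pre-specified tables, including NC = M, NC = F and the Week 24 comparison. Beside the NC = M off-treatment tables:

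1. Show the number of subjects who have restarted anti-HBV therapy at each off-treatment visit.
2. Add a supplementary version of sustained HBeAg seroconversion (after Week 48, and for the Post-Year 1 groups) and of the 7.5.8 response rates. In it, each scheduled visit after restart that falls within study follow-up is a non-response; visits missing for other reasons, or not yet reached, stay missing.
3. Add a restarted-therapy category to the HBV DNA, ALT and response-shift tables.

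State in the SAP that the supplementary version also counts as failures the children who restart while still seroconverted. In the random-restart example above it would show 0.70 × 0.80 = 56% where 70% is right. The two versions should therefore be read together.

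The cost is SAP wording, one flag from the restart date already derived in 8.9, and extra columns and one category. No new data are collected and nothing planned is removed. The drawback is a second, less favourable rate that needs this explanation.

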### **7.5.9 Histology**

Histological parameters are listed, including most recent liver biopsy date, scoring system (Knodell, Ishak, Metavir, other), hepatitis activity index, fibrosis score and findings.

### **7.5.10 Genotypic Resistance**

Analyses of genotypic resistance will be addressed in a separate integrated resistance SAP for studies AI463-028 and AI463-189.

## **7.6 Safety**

The investigators determine the intensity of AEs and the relationship of AEs to study therapy. The investigators' terms are coded and grouped by system organ class using the latest version of the Medical Dictionary for Regulatory Activities (MedDRA) in production at BMS.

In order to account for AEs with multiple occurrences in the same subject, AE records are collapsed for each subject and preferred term when records have the same onset date, or when records are contiguous or overlapping (see [Section 8.10](#)). All AE presentations are based on collapsed records.

AEs are presented by system organ class and preferred term, both in descending order of incidence on ETV, unless specified otherwise.

AE presentations include both non-serious and SAEs as defined in the protocol, unless specified otherwise. If a subject had an AE with different intensities during the study period, then only the greatest intensity is reported.

On-treatment safety is assessed for the following 3 cohorts (see [Sections 6.1](#) and [6.3](#)):

- Through Week 48 on blinded therapy for treated subjects
  - ETV and PBO are assessed on treatment up to the Week 48 cut, ie, the earlier of (a) 54 weeks, the upper bound of the Week 48 visit window (see [Section 8.4](#)), and (b) the first dose of open-label ETV.
- After Week 48 on blinded therapy or on open-label ETV through Week 96 for the Year 2 Safety Cohort

- ETV, PBO BL and PBO OL are assessed on treatment after the Week 48 cut and up to 102 weeks, the upper bound of the Week 96 visit window (see [Section 8.4](#)).
- On ETV treatment for All ETV Safety Cohort

Note that AEs with onset on the first day of study therapy are considered on treatment, AEs with onset on the first day of ETV are considered on ETV treatment and AEs with onset on the first day of open-label ETV are considered on open-label ETV.

Follow-up safety is assessed for the following 3 cohorts (see [Sections 6.1](#) and [6.3](#)):

- During off-treatment follow-up for off-treatment follow-up subjects in the Post-Year 1 Safety Cohort
- During long-term follow-up for long-term follow-up subjects in the Post-Year 1 Safety Cohort.
- During alternative ETV follow-up for alternative ETV follow-up subjects in the Post-Year 1 Safety Cohort (select endpoints only).

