5.3.2 Other Guidance

5.3.2.1 Study Subject Management for ALT Elevations or Hepatic Clinical Events

Acute exacerbation of hepatitis B (ALT > 2 x baseline AND > 10 x ULN) and hepatic clinical events may represent a critical scenario with the potential for serious hepatic injury and death. Guidelines for managing these events can be found in [Figures 5.3.2.1](#). Should an event as described occur, a blood sample for HBV DNA determination using a sensitive PCR technique should be obtained and sent to the central laboratory for this study. If results are needed urgently for patient management decisions, a sample should be also drawn and concurrently sent to a local laboratory for assessment. An unscheduled visit laboratory kit should be used for the HBV DNA sample if it is collected at a time that is not required by the protocol. Non-HBV related potential causes of worsening hepatitis also need to be considered (hepatitis A, C, D, concomitant medications, etc).

Figure 5.3.2.1: Management of Significant Elevations of Serum ALT Due to the Acute Exacerbation of Chronic Hepatitis B

¹ Clinical manifestations suggestive of hepatic complications include but are not limited to: Ascites, Hepatic encephalopathy, Increasing nausea, vomiting, or abdominal pain, Jaundice, Variceal bleeding, etc.

² Laboratory findings that may be suggestive of evolving liver dysfunction include but are not limited to: Increasing INR, Total bilirubin, or Serum lactate levels, or Declining serum albumin values.

³ Subjects experiencing acute exacerbation of CHB resulting in ALT flare WITH clinical or laboratory findings suggestive of liver dysfunction or other serious safety concern may be eligible for rescue open-label ETV as determined on a case-by-case basis following consultation with the BMS Central Medical Monitor.

⁴ Labs may be processed by local or central laboratory. An unscheduled visit laboratory kit should be used if labs are collected at a time that is not required by the protocol.

⁵ Subjects placed on rescue open-label ETV will be immediately placed into the study's LTFU phase. Protocol visits should be scheduled as described in Section 6.1. Patients who are provided rescue open-label ETV to treat an extreme elevation of ALT due to acute exacerbation of CHB should undergo additional non-protocol visits and assessments at the discretion of the managing investigator. See section 4.1.2.

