7.3.1 Serious Adverse Events

Following the subject's written consent to participate in the study, all SAEs must be collected, including those thought to be associated with protocol-specified procedures. All SAEs must be collected that occur within 30 days of discontinuation of dosing or within 30 days of the last visit for screen failures. If applicable, SAEs must be collected that relate to any later protocol-specified procedure (eg, a follow-up skin biopsy).

The investigator should notify BMS of any SAE occurring after these time periods that is believed to be related to study drug or protocol-specified procedure.

Serious Adverse Events should be reported during the long-term follow up phase, regardless of whether or not the subjects are receiving commercially available anti-HBV therapy. Any medical event that the investigator considers to be "medically important" in the context of pediatric drug exposure (for example neurodevelopmental delay), may be reported as an SAE under the category "Important Medical Event." (see Section 7.1.1)

Serious adverse events, whether related or unrelated to study drug, must be recorded on the SAE page of the CRF and reported within 24 hours to BMS (or designee) to comply with regulatory requirements. An SAE report should be completed for any event where doubt exists regarding its status of seriousness.

All SAEs must be reported within 24 hours by confirmed facsimile transmission (fax) or scanned and reported via electronic mail. (Note: Follow-up SAE reports should include the same investigator term(s) initially reported.) In selected circumstances, the protocol may specify conditions that require additional telephone reporting. The SAE electronic CRF in the electronic data capture tool should not be used.

If the investigator believes that an SAE is not related to study drug, but is potentially related to the conditions of the study (such as withdrawal of previous therapy, or a complication of a study procedure), the relationship should be specified in the narrative section of the SAE page of the CRF.

If an ongoing SAE changes in its intensity or relationship to study drug, a follow-up SAE report should be sent within 24 hours to the sponsor. As follow-up information becomes available it should be sent within 24 hours using the same procedure used for transmitting the initial SAE report. All SAEs should be followed to resolution or stabilization.

SAE FACSIMILE TRANSMISSION:

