## 4.3 Other Secondary Endpoints

- The number and percent of subjects with adverse events (including palatability issues), serious adverse events (SAEs), discontinuations due to adverse events, and HBV disease progression through Week 48;
- Proportions of subjects with HBeAg loss at Weeks 48 and 96;
- Proportion of subjects with HBeAg seroconversion at Week 96;
- Proportion of subjects who maintained HBeAg seroconversion at Week 96 (end of blinded therapy) among subjects who achieved HBeAg seroconversion at Week 48;
- Histological analysis among subjects with available liver biopsy.

[REDACTED]

- [REDACTED]

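### New serious events and later liver-test peaks after early stopping or rescue are missing from the Week 48 safety comparison, which ends at last study dose plus 5 days

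*SAP*

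**What the plan says.** SAP 4.3, matching Protocol 8.3, makes it a secondary endpoint to report the number and percent of subjects with adverse events, "serious adverse events (SAEs), discontinuations due to adverse events, and HBV disease progression through Week 48". The wording has no on-treatment limit.

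The limit comes from the analysis sections:

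- SAP 7.6: "ETV and PBO are assessed on treatment up to the Week 48 cut". The cut is the earlier of "54 weeks, the upper bound of the Week 48 visit window" and the first dose of open-label entecavir (ETV). SAP 7.6.2 and 7.6.6.1 use this period for SAEs and laboratory abnormalities.
- SAP 6.1: the on-treatment period "ends at the last dose of study therapy plus 5 days".
- SAP 6.1: "Note that rescue open-label ETV is considered alternative anti-HBV therapy". SAP 8.9 leaves rescue ETV out of every dose-date derivation.
- Protocol 5.3.2.1, footnote 5 to the figure: "Subjects placed on rescue open-label ETV will be immediately placed into the study" long-term follow-up (LTFU) phase.

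Protocol 8.4.2 reports SAEs and deaths for enrolled subjects whatever their treatment status, and applies the 5-day period to the other safety evaluations. SAP 6.3 and 7.6.2 use the enrolled cohort for SAEs only before treatment.

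**The concern.** Children without HBeAg seroconversion move to open-label ETV at Week 52. The Week 48 table is therefore the main placebo-controlled comparison of AEs and SAEs.

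Randomisation protects a count over a fixed period. It does not protect a count that ends when a child stops drug because of a harm, and stopping for a flare could well differ between treated and untreated children. In the number-and-percent table the child stays in the denominator but can add no new event after day 5.

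The plan foresees rescue before Week 48. SAP 7.5.1 has an efficacy sensitivity analysis for placebo children who start it by then. Safety has no counterpart.

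**Working it through.** **Stated figure.** The plan gives no figure for the safety comparison. The efficacy sample size reproduces (two proportions, 1% v 20%, two-sided 0.05, 2:1, pooled variance: 41 + 82 = 123, power 90.4%) and is not affected.

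**Where a post-rescue event goes.** Take a child whose last study dose is at week 24, who then starts rescue and has a new SAE at week 30.

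- Week 48 SAE table (SAP 7.6.2): not counted, because onset is after last dose plus 5 days.
- Off-treatment follow-up table: not counted, because that period ends the day before alternative therapy starts (SAP 6.1).
- LTFU and alternative-ETV follow-up tables: counted by regimen. These cover only children who reached those periods, and they run to the end of study.
- Death summary (SAP 7.6.1): counted if fatal, since study period is ignored, but with no Week 48 limit.
- HBV disease progression (SAP 7.6.4.1): counted if the term is listed (ascites, hepatic encephalopathy and hepatorenal syndrome are; hepatic failure and jaundice are not), over on-treatment and LTFU combined.
- Same preferred term as an on-treatment event, with contiguous or overlapping records: collapsed to the earlier onset with the highest intensity and SAE status (SAP 8.10), so counted.

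The gap is therefore new-onset SAEs under other terms, and laboratory peaks after the cut.

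**Days uncounted per child.** The window is 54 × 7 = 378 days. With the last study dose at the end of week w, days uncounted = 378 − (7w + 5).

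| Last dose, week | Days uncounted | Share of 378 |
|---|---|---|
| 4 | 378 − 33 = 345 | 91% |
| 12 | 378 − 89 = 289 | 76% |
| 24 | 378 − 173 = 205 | 54% |
| 36 | 378 − 257 = 121 | 32% |
| 44 | 378 − 313 = 65 | 17% |

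Many children will have their own cut at the Week 52 switch. Against day 364 the week-24 loss is 364 − 173 = 191 days.

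**Events missed (assumed inputs).** No rescue rate is stated. Assume 2% to 10% of the 60 planned placebo children are rescued, each with a 10% to 50% chance of a new serious event in the gap.

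- Low end: 60 × 0.02 × 0.10 = 0.12 events; chance of at least one = 1 − 0.998^60 = 11%.
- High end: 60 × 0.10 × 0.50 = 3.0 events; chance of at least one = 1 − 0.95^60 = 95%.

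One event among 60 children is 1.7%.

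**The 10% condition.** SAP 9 shows follow-up safety at the primary analysis only if at least 10% of treated subjects have post-dosing data: 13 of 123, or 18 of 180. Accrual of 82 ETV children over 104 weeks puts the analysis near study week 104 + 48 = 152. About 82 × 50/104 = 39 of them will then be at least 102 weeks from entry. If 20% continue treatment (assumed), about 31 have stopped, so the condition would probably be met.

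**The case against.** The strongest reply is that little is really lost. The flare that triggers rescue normally starts on study drug and enters the on-treatment ALT-flare summary. Deaths, disease progression and same-term worsening are kept. Post-rescue events are tabulated by regimen, and every child with a flare has ALT and HBV DNA plotted (SAP 7.6.6.1). Exposure-adjusted rates use time on study therapy plus 5 days, so there a rescued child leaves the denominator too. All of this stands, and it limits the point to the gap described above. It does not close that gap: an exposure-adjusted rate is still cut off by the harm, and the follow-up tables mix calendar and treatment periods.

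A second reply is that the 5-day window is the protocol's own. That is true for non-serious events and laboratory data. It is not true for SAEs under Protocol 8.4.2.

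A reader might infer that the later course of the main known harm vanishes from the only randomised safety comparison. The documents do not support that. Deaths, progression and malignant neoplasms are also shown by regimen, and Protocol 1.5 says its risk assessment is mainly about pre-clinical findings. A reader might also set the 5 days against Protocol 7.3.1 ("All SAEs must be collected that occur within 30 days of discontinuation of dosing"). That is a rule for collecting data, not for analysing it. Nor does the omission necessarily flatter ETV: if rescue is commoner on placebo, placebo harm is understated.

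**Conclusion.** The point holds in limited form, as a cheap improvement. The endpoint wording and its analysis do not match, and no planned table gives SAEs by arm to Week 48 regardless of dosing. The lost time per child follows from the plan's rules: 65 to 345 of 378 days for a last dose between weeks 44 and 4. The number of missed events cannot be derived. The range of 0.12 to 3.0 rests wholly on assumed rescue and event rates. The conclusion does not depend on the 10% condition or on the 30-day collection window.

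**What to change.** Keep the on-treatment table. Add to SAP 7.6.2 and 7.6.6.1 a supplementary table by randomised arm for all treated subjects, which:

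- counts SAEs and deaths, and ALT flares with the other select liver laboratory abnormalities;
- runs from first dose to the earlier of 54 weeks and first protocol open-label ETV, whether or not blinded therapy was stopped or rescue started;
- flags events after the start of rescue;
- is shown at the primary analysis without the 10% condition.

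Do not extend it to non-serious Grade 3-4 AEs, or show these only with a note that capture is unequal. In LTFU all AEs are recorded only for children on rescue. For others, only events related to giving or stopping study drug are recorded, and only if the child is not on commercial anti-HBV therapy (Protocol 6.3.2 and 7.3.3).

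The cost is one extra table set from data already collected: SAEs are reported throughout LTFU (Protocol 7.3.1), and chemistry continues there on schedule (Protocol Table 6.1). The drawback is that it includes some events after rescue ETV, which the flag makes visible. No clinical rule changes.
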